## Gastroparesis Registry 2 Protocol

### 7. Statistical and design considerations

---

As noted earlier, the Gastroparesis Registry 2 is a prospective, multi-center, observational study with standardized collection of data on a large cohort of patients with gastroparesis or gastroparesis-like symptoms. The overall objective is to broadly compile baseline and follow-up data, including biospecimens and DNA, on the cohort with the aim of better defining the epidemiology, etiology, and natural history of gastroparesis. In addition, the GpR 2 will serve as a major patient recruitment source for randomized, controlled clinical trials of treatments for gastroparesis. The recruitment goal for the GpR 2 is to enroll over a 30 month period, a total of 500 patients consisting of 270 new patients and 230 patients continuing from the first Gastroparesis Registry. One or more years of follow-up data will be collected on each enrolled patient.

As this is the largest cohort study of gastroparesis, the objectives and hypotheses to be examined are intentionally numerous and cut across many aspects of gastroparesis (e.g., see Section 2). Furthermore, new hypotheses and objectives, not listed in Section 2, are expected to arise later in the study. These might arise as follow-up analyses suggested by information from GpR 2 data analyses related to the objectives and hypotheses in Section 2 or from new information from sources outside the GpCRC. This approach mirrors the successful process that occurred during the first phase of the GpR, in which presentations and publications from accumulating data were made, rather than waiting until the recruitment goal was met.

Addressing the specified hypotheses of the GpR 2 using the multicenter, multivariable, longitudinal cohort data will require a full array of statistical analyses ranging from simple descriptive statistics to multivariable regression models applied to either cross-sectional data or longitudinal data. Given this diversity of analytic plans, it is not possible to have one global sample size calculation for the GpR 2. However, as was done successfully in the first phase of the GpR, proposers of every presentation or publication related to one of the study aims must submit a formal Abstract/Manuscript (AMP) or Study Proposal (SP) application form to the GpCRC Steering Committee stating the aims, rationale, methods and materials needed (e.g., biospecimens or DNA) and giving a detailed statistical plan, including a sample size justification. Every proposal must identify appropriate subgroups of patients for analysis and comparison, drawing patients from all clinical centers. Analyses tailored to the hypotheses to be addressed must also be included in the proposal. For each proposal, the Steering Committee approves, disapproves, or suggests modifications and resubmission to the proposers.

For each publication or ancillary study proposed to the Steering Committee the following considerations must be addressed to ensure that the sample size results in an adequately powered analysis to address the primary aim of the proposal.

- Statement of the hypothesis to be addressed with references to the Protocol,
- Specification of the primary outcome measure for the hypothesis,
- Specification of Type I error  $< 0.05$  and power  $\geq 0.80$  in sample size determination,
- Specification of primary comparison groups and outcome measures,
- Specification of minimum clinically meaningful effect size for the primary outcome,
- Specification of inclusion/exclusion criteria needed to define the subgroup of Registry patients needed for the hypothesis,
- Specification of methods for handling missing data,
- Specification of adjustments for multiplicity,
- Specification of the method of statistical analysis for primary and secondary objectives

The sample size must be justified by calculations (using PASS 2011 or similar design software), which will include the relative sizes of the subgroups for comparisons (rarely will the ratio be 1:1), Type I error of 0.05 or less, a power of 0.80 or higher, specification of a clinically meaningful effect size, and estimated event rates (categorical outcomes) or estimates of variability (e.g., SD of primary outcome measure), and a rationale for achievement of the sample size in a reasonable period of time, either from existing patients in the registry or from patients to be recruited in the future, or both, and, if appropriate, adjustments for missing data. Adjustments to Type I errors for multiplicity of comparisons are not needed for hypotheses pre-specified in Section 2.1. Other hypotheses that are not pre-specified and that arise as a result of data analyses will be identified in publications as exploratory and needing further confirmatory data.

As noted above, each publication or presentation requires a separate statistical plan and sample size justification; however, it is useful to illustrate the statistical power and minimum clinical meaningful effect sizes that will be detectable for a few major subgroups. Table 5 shows four major subgroup comparisons reflecting the expected patient mix of the target 500 patients in the GpR 2: (1) patients with delayed (n=400) vs. not delayed (n=100) gastric emptying, and, among the patients with delayed gastric emptying, (2) diabetic (n=120) vs. idiopathic (n=200), (3) Type 2 (n=50) vs. Type 1 (n=70) diabetics, and (4)

patients with post-Nissen fundoplication (n=80) vs other types of gastroparesis (n=320). These examples provide a mix of small, intermediate, and large subgroups for comparison, which represent the range of subgroup sizes likely to arise in GpR 2 analyses related to study aims and objectives. The type of outcome measure that must be analyzed to address a particular study aim influences the sample size considerations.

Both categorical (either binary or more than 2 categories) and continuous or quasi-continuous (ordered) outcome measures may be needed. The sample size is strongly dependent on the event rates (for binary categorical outcomes) or, for continuous outcome measures, the variability, expressed in standard deviation (SD) units. Using the extensive database collected during the first phase of the GpR, we developed estimates useful for study planning in GpR 2. These estimates are shown in Table 6 (for continuous outcomes) and Table 7 (for binary outcomes). Potential outcome measures shown in Tables 6 and 7 may be used either in cross-sectional analyses (baseline data) or longitudinal data analyses (baseline and repeated follow-up measures).

Table 6 presents the measures of variability and the minimal clinically important effect sizes (in  $SD_{\Delta}$  units) for continuous outcome measures of direct interest in GpR 2: PAGI-SYM, GCSI and related subscales, six measures of quality of life and/or depression, BMI, three laboratory measures from serum, and two and four hour gastric emptying times. The following information for each of several potential outcome measures is displayed: the overall mean at baseline, the standard deviation of the measure at baseline ( $SD_b$ ), the coefficient of variation ( $CV = SD_b/\text{mean}_b$ ), and for longitudinal studies,  $SD_{\Delta}$ , the standard deviation of the change in the measure from baseline to follow-up, and the

**Table 5. Illustrative GpR 2 Subgroup Comparisons**

Major Subgroup Comparisons	Expected Subgroup Size	
	Smaller	Larger
Delayed Gastric Retention: No vs Yes	100	400
Patients with Delayed Gastric Retention:		
Diabetic vs. Idiopathic	120	200
Diabetes: Type 2 vs Type 1	50	70
Post-Nissen vs Other Gastroparesis	80	320

intra-class correlation coefficient of repeated within-person measures ( $r$ ). GpR 2 analyses of baseline or follow-up data using more variable outcome measures such as total hospitalizations ( $CV=2.0$ ), C-reactive protein ( $CV=1.7$ ), or 2-hr ( $CV=0.7$ ) or 4-hr ( $CV=0.9$ ) gastric emptying times will need larger sample sizes than studies using less variable outcomes such as GSCI ( $CV=0.4$ ), the SF-36 quality of life scales ( $CV=0.3$ ), or HbA1c ( $CV=0.2$ ).

Table 6 also shows, for each potential outcome measure, the minimum clinically important effect size (in SD units) detectable with 80% statistical power and 0.05 two-sided Type I error for four subgroup comparisons with longitudinal outcome measures of change from baseline to 48 weeks, where the smaller subgroup ranges across the sizes shown in Table 5: (1) Diabetes mellitus vs. idiopathic groups, (2) Type 2 vs. Type 1 diabetes, (3) Post Nissen fundoplication vs. other gastroparesis, and (4) Patients with gastroparesis symptoms without vs. with delayed 4 hour gastric emptying by scintigraphy. In every case, across outcomes measures and subgroup sizes, the GpR 2 sample size provides adequate power to detect minimum clinically important effect sizes of  $0.5 SD_{\Delta}$ , or smaller; the smallest effect size is  $0.10 SD_{\Delta}$  and the average effect size in the Table 6 is  $0.30 SD_{\Delta}$ .

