## Gastroparesis Registry 2 Protocol

**Table 6: Measures of Variability and Minimum Clinically Important Effect Sizes (in  $SD_{\Delta}$  units) detectable with 80% power and 0.05 Type I error for Changes in Continuous Outcome Measures from Baseline to 48 Weeks**

Continuous Outcomes	Mean*	$SD_b$ †	CV†	$\Delta$ †	$SD_{\Delta}$ †	r†	Smaller Subgroup‡§			
							DM	T2DM	Post-Nissen	Not Delayed
							MDE	MDE	MDE	MDE
Symptoms:										
PAGI-SYM: (0-5)										
GCSI	2.9	1.0	0.4	-0.4	1.1	0.44	0.34	0.55	0.37	0.33
Nausea/Vomiting Sub-scale	2.5	1.4	0.6	-0.4	1.4	0.56	0.31	0.50	0.34	0.30
Postprandial Fullness Sub-scale	3.4	1.1	0.3	-0.6	1.3	0.31	0.38	0.62	0.41	0.37
Bloating Sub-scale	3.0	1.6	0.5	-0.2	1.5	0.57	0.30	0.48	0.32	0.29
Upper abdominal sub-score	3.0	1.6	0.5	-0.5	1.5	0.53	0.29	0.48	0.32	0.29
Total hospitalizations in past year	1.9	3.9	2.0	-0.4	3.2	0.66	0.22	0.35	0.24	0.22
Depression/Quality of Life										
BDI score (0-63)	18.8	11.2	0.6	-0.5	9.9	0.61	0.26	0.40	0.28	0.25
State anxiety score (0-80)	44.7	13.6	0.3	0.2	13.9	0.48	0.28	0.46	0.30	0.27
Trait anxiety score (0-80)	44.0	12.5	0.3	0.4	10.8	0.63	0.25	0.40	0.27	0.25
PAGI-QOL total score (0-5)	2.5	1.1	0.4	0.3	0.9	0.64	0.25	0.40	0.26	0.24
SF-36 physical component (0-100)	33.7	10.5	0.3	1.7	9.4	0.60	0.26	0.41	0.28	0.25
SF-36 mental component (0-100)	37.9	12.8	0.3	1.5	12.1	0.56	0.27	0.43	0.29	0.26
Anthropometric:										
BMI kg/m 	27.0	7.3	0.3	0.5	2.6	0.94	0.11	0.18	0.12	0.11
Laboratory measures:										
C-reactive protein (CRP) mg/dL	0.7	1.2	1.7	0.8	0.4	0.95	0.10	0.16	0.11	0.10
ESR (mm/hr)	18.3	19.0	1.0	1.0	15.1	0.69	0.23	0.37	0.25	0.23
HbA1c (%) (for Diabetics only)	7.9	1.9	0.2	0.2	1.9	0.48	n/a	0.46	n/a	n/a
Gastric emptying (scintigraphy):										
% retention at 2 hours	55.4	23.4	0.7	7.0	22.2	0.55	0.27	0.43	0.29	0.26
% retention at 4 hours	25.1	23.4	0.9	6.7	21.2	0.59	0.26	0.42	0.28	0.25

\* Based on data from the GpR Phase I (N=570 participants)

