†  $SD_b$  defined as standard deviation (SD) of the mean baseline outcome; CV defined as the coefficient of variation of the baseline outcome data;  $\Delta$  defined as the mean change in outcome from baseline to 48 weeks;  $SD_{\Delta}$  defined as the SD of the change in the outcome measure at 48 weeks; r defined as the intra-class correlation of the measure across time; MDE defined as the minimal detectable effect size (in  $SD_{\Delta}$  units) at 80% power, 0.05 type I error, and r, the correlation between baseline and 48 week measures.

‡ The smaller subgroup is compared to the larger one: DM is all diabetes (N=120) vs idiopathic (N=200), T2DM is Type 2 Diabetes (N=50) vs Type 1 (N=70), Post-Nissen is Post Nissen Fundoplication (N=80) vs others with gastroparesis (N=320); all 6 subgroups must have delayed retention at 4 hour on baseline GES. Not Delayed (N=100) vs Delayed retention (N=400) at 4 hour baseline GES.

§ MDE, expressed in  $SD_{\Delta}$  units, determined from Stata v12 software's "Sample size and power determination for tests of means with repeated measures" (*sampsi\_repmeas*) and the method, ANCOVA, correcting for the mean at baseline. Conversion of the MDE to units of the outcome is computed by multiplying the MDE in Table 6 by  $\Delta$  (mean change of outcome).

As a further aid to sample size justification for analyses related to GpR 2 aims, Figure 1, Panel A shows detectable effect sizes in multiples of SD as a function of the size of the smaller of two subgroups with Type I error = 0.05 and 3 choices for statistical power: 0.50 (inadequate power), 0.80 (good power), and 0.90 (excellent power). Given the subgroup size in the smaller comparison group vs a larger subgroup ( $500 - N_{\text{smaller}}$ ) and outcome measure of interest, Panel A of Figure 1 can be used to find the minimum clinically important detectable effect in SD units; the effect size can be easily converted to the units of the outcome measure of interest using Table 6 (see footnote §).

If the comparison subgroup size is smaller than specified above, then the power will be less than 0.80 for that detectable effect size, or fixing the power at 0.80, the detectable effect size will be larger.

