Other studies may require categorical outcomes rather than continuous outcomes. In most cases, a binary event can be defined as the outcome measure in order to judge the adequacy of the sample size, which depends on the Type I error, power, sizes of the subgroups to be compared, and the event rate in the reference subgroup. Table 7 contains information on event rates in reference groups for comparisons of important categorical outcome measures derived from the database from the first phase of the GpR, some of which indicate

improvement over time at 48 weeks (GCSI, PAGI-QOL, SF-36, BDI) and others indicate status at baseline (gastric failure, BMI category, CRP/ESR inflammatory markers, and degree of gastric retention). This mix of important variables is not exhaustive, but the general approach illustrated applies to other categorical outcomes not in Table 7.

**Figure 1. (A) Detectable Effect Size (in SD units) with Power = 0.90, 0.80 and 0.50 and (B) Detectable Relative Risk with Power = 0.80 and Reference Group Effect Rates of 0.5, 0.3 and 0.1 for Analyses Comparing Two Subgroups with Type I error = 0.05 and Total Sample Size of 500**

[figure not shown]

Table 7. Event Rates for Binary Outcome Measures in Reference Subgroups of Interest

Binary Outcomes	Smaller Subgroup*			Not Delayed‡
	Gastroparesis			
	Diabetes	T2DM	Post-Nissen†	
	Rate	Rate	Rate	Rate
Improvement at 48 weeks from baseline:				
Improvement in GCSI (- 0.75 point or less)	0.32	0.29	0.27	0.39
Improvement in PAGA-QOL (0.5 point or more)	0.32	0.30	0.17	0.48
Improvement in SF-36 mental (3.0 points or more)	0.42	0.40	0.33	0.43
Improvement in SF-36 physical (3.0 points or more)	0.42	0.47	0.50	0.41
Improvement in BDI (-5.0 points or less)	0.26	0.24	0.23	0.26
At baseline:				
Gastric failure vs Mild/Compensated	0.44	0.39	0.41	0.22
Not overweight (BMI > 25 kg/m  ) vs Overweight	0.34	0.14	0.71	0.39
Inflammation§ vs not	0.55	0.57	0.35	0.35
Severe 4 hr Gastric Retention vs < 35% retention	0.45	0.32	0.52	n/a

\* The smaller subgroup is compared to the larger one: DM is all diabetes (N=120) vs idiopathic (N=200), T2DM is Type 2 Diabetes (N=50) vs Type 1 (N=70), Post-Nissen is Post Nissen Fundoplication (N=80) vs others with gastroparesis (N=320); all 6 subgroups must have delayed retention at 4 hr on baseline GES. Not Delayed (N=100) vs Delayed retention (N=400) at 4 hour baseline GES.

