† Post-Nissen Fundoplication subgroup outcome distributions estimated from the GpR post-surgical group (N=23).

‡ Delayed emptying defined as % gastric retention on scintigraphy at 2 hrs >60% OR gastric retention at 4 hrs > 10%

§ Inflammation defined as CRP > 1.0 mg/dL and /or ESR > 20 mm/hr

¶ Event rates > 0.5: Use 1 – (event rate) to determine power for a given detectable relative risk in Figure 1, Panel B

The event rates in Table 7 can be used in combination with Figure 1, Panel B to find the minimum clinically important relative risk when comparing two subgroups of varying sizes with power = 0.80 and Type I error = 0.05. Detection of relative risks of 2.0 or smaller is possible for event rates near 0.5, even for subgroups as small as 100. Similar sizes of subgroups are needed for event rates near 0.3; if the event rate is as low as 0.1, only relative risks greater than 2.5 will be detectable. Since for this graph, the 2 subgroup sizes must add to 500, then if the combined subgroup size is smaller than 500, the power to detect that relative risk will be less than 0.80.

The calculations presented in Figure 1 assumed two-sided Type I error = 0.05, and a total sample size = 500. The detectable effect size plot in Panel A of Figure 1 assumed power of 0.5, 0.8, and 0.9, and used as the test statistic an ANCOVA with a correlation between baseline and follow-up measures = 0.5 and used Stata (StataCorp 2011. Stata Statistical Software: Release 12. College Station, TX: StataCorp LP) for the calculations. The detectable relative risk plot in Panel B of Figure 1 assumed power = 0.80 and an uncorrected chi-square as the test statistic using the sample size

software of Dupont and Plummer (Dupont W, Plummer WD: Power and Sample Size Calculations: A Review and Computer Program, Controlled Clinical Trials 1990; 11:116-28).

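### Table 6 contradicts the claim that every comparison can detect 0.5 SD or less, and its six symptom rows do not follow the ANCOVA method named in its footnote

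*Protocol*

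**What the plan says.** Section 7 introduces Table 6 as giving effect sizes "detectable with 80% statistical power and 0.05 two-sided Type I error for four subgroup comparisons", for change from baseline to 48 weeks. It then concludes: "In every case, across outcomes measures and subgroup sizes, the GpR 2 sample size provides adequate power to detect" minimum clinically important effects of 0.5 SD_Δ or smaller, with a smallest value of 0.10 and an average of 0.30.

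Footnote § to Table 6 names the Stata routine and "the method, ANCOVA, correcting for the mean at baseline". Footnote † defines the MDE in SD_Δ units and says that it uses r, "the correlation between baseline and 48 week measures".

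In the Type 2 versus Type 1 column, Table 6 prints 0.55 for GCSI and 0.62 in the row "Postprandial Fullness Sub-scale".

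Two smaller entries belong with this. The 2-hour retention row has mean 55.4, SD 23.4 and CV 0.7, and the text repeats the 0.7. Table 7 has a row labelled "Not overweight (BMI > 25 kg/m"²) set against overweight.

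**The concern.** The sentence is universal and two cells in the table it describes break it. Two of the printed values also exceed what the comparison would need with no baseline adjustment at all. Adjusting for baseline cannot make the detectable effect larger, so the stated method cannot have produced them.

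Symptom scores are central outcomes of this registry. Section 7 sends proposers to Table 6 for planning values, and every proposal must carry its own sample size justification. An error here can therefore be copied into later proposals. Most of the symptom rows would make a proposer ask for too many patients; the hospitalization row would make one ask for too few.

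**Working it through.** **Inputs.** Two-sided 0.05 and 80% power (Section 7), so z = 1.960 + 0.842 = 2.802. Group sizes are from Table 6 footnote ‡, and r and the printed MDEs from Table 6.

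**Unadjusted MDE**, 2.802 × √(1/n₁ + 1/n₂), in outcome SD units:
- Diabetic vs idiopathic, 120 vs 200: 0.323
- Type 2 vs Type 1, 50 vs 70: 0.519
- Post-Nissen vs other, 80 vs 320: 0.350
- Not delayed vs delayed, 100 vs 400: 0.313

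**Formulas.** ANCOVA multiplies these by √(1 − r²), which is at most 1. A change score without baseline adjustment multiplies them by √(2(1 − r)), which exceeds 1 when r is below 0.5.

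**The protocol's own summary.** The 69 printed MDEs have minimum 0.10 and mean 0.303, as the text says. The maximum is 0.62, and exactly two cells exceed 0.5.

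**Non-symptom rows.** ANCOVA reproduces 44 of 45 cells within 0.01. The other is BDI, Type 2 vs Type 1: 0.411 against 0.40 printed.

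**Symptom rows** (order: diabetic / Type 2 / post-Nissen / not delayed):

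| Row (r) | Printed | ANCOVA | Change score |
|---|---|---|---|
| GCSI (0.44) | .34 / .55 / .37 / .33 | .291 / .466 / .314 / .281 | .342 / .549 / .371 / .331 |
| Nausea/vomiting (0.56) | .31 / .50 / .34 / .30 | .268 / .430 / .290 / .260 | .303 / .487 / .329 / .294 |
| Fullness (0.31) | .38 / .62 / .41 / .37 | .308 / .493 / .333 / .298 | .380 / .609 / .411 / .368 |
| Bloating (0.57) | .30 / .48 / .32 / .29 | .266 / .426 / .288 / .257 | .300 / .481 / .325 / .290 |
| Upper abdominal (0.53) | .29 / .48 / .32 / .29 | .274 / .440 / .297 / .266 | .314 / .503 / .340 / .304 |
| Hospitalizations (0.66) | .22 / .35 / .24 / .22 | .243 / .390 / .263 / .235 | .267 / .428 / .289 / .258 |

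None of the 24 printed cells is within 0.01 of ANCOVA. GCSI and bloating match the change score. Fullness and nausea/vomiting are within about 0.013 of it. Upper abdominal lies between the two formulas, and hospitalizations lies below both.

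**Check inside the table.** Nausea/vomiting and SF-36 mental have the same r (0.56) and the same groups. They print .31 / .50 / .34 / .30 and .27 / .43 / .29 / .26. One method cannot give both.

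**Rounding.** Rounding of r does not explain the gaps. For 50 vs 70, no r takes ANCOVA above 0.519, so 0.55 and 0.62 are out of reach.

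**Power at 0.5 SD from the printed MDEs**, Φ(2.802 × 0.5/MDE − 1.960):
- MDE 0.55: Φ(0.587) = 72%
- MDE 0.62: Φ(0.299) = 62%

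**Units.** The ANCOVA values that reproduce the table are in baseline SD units, not SD_Δ as labelled. Conversion to SD_Δ replaces the factor by √((1 + r)/2). This is also at most 1, so relabelling does not rescue 0.55 or 0.62. In SD_Δ units the Type 2 vs Type 1 values for BMI and CRP would be about 0.51 (0.50 and 0.49 with the rounded tabulated SDs), against 0.18 and 0.16 printed.

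**After recomputing all rows by ANCOVA with the printed r:** maximum 0.493, mean 0.29.

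**2-hour retention.** 23.4/55.4 = 0.42, against 0.7 printed.

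**The case against.** The strongest defence is that nothing in the registry rests on Table 6. Section 7 says that no single sample size calculation is possible, presents these figures as illustrations, and requires a justification in every proposal. Only 2 of 69 cells break the sentence; both are in the smallest comparison and printed openly. Five of the six symptom rows err on the cautious side, and under the stated method the sentence becomes true. All of this stands. It limits the weight of the point, but does not make the sentence or the rows correct as printed.

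It is also fair to say that the documents do not show which input is wrong in every row. For upper abdominal, a change score with r = 0.57 in place of the printed 0.53 gives .30 / .48 / .32 / .29, almost the printed row. A wrong r, or values carried over from bloating, is possible. For 2-hour retention, the mean, the SD or the CV could be at fault.

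Two stronger readings are tempting and are not supported:
- A reader might infer that the power claim fails even after correction once patients are lost before week 48. That depends on a loss rate the protocol does not give, and Section 7 leaves missing-data methods and adjustments to each proposal. What can be said is that the table assumes complete data.
- A reader might infer that the relative-risk text is wrong too. The statement that 2.0 or smaller is detectable at event rates near 0.5, and similarly near 0.3, is a loose bound but a true one: at 100 vs 400 the detectable values are about 1.31 and 1.50. The clause "if the event rate is as low as 0.1, only relative risks greater than 2.5 will be detectable" names no subgroup size of its own, and about 2.5 is what results at roughly 50–60 vs 440–450. The figure behind it is not available to check.

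**Conclusion.** The point holds in a limited form, and the text should be corrected. The sentence that every comparison reaches 0.5 SD_Δ or smaller is false against the printed table, for GCSI and fullness in Type 2 versus Type 1 diabetes only. None of the six symptom rows follows the method in footnote §, while essentially all other rows do. Five of the six print detectable effects larger than ANCOVA gives; hospitalizations prints smaller ones.

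The sample size of 500 is not called into question. With the printed r, the stated ANCOVA and full subgroups with complete 48-week data, the largest MDE is 0.49 in baseline SD units, so the sentence would then hold in those units. Relabelled as SD_Δ it would be borderline, because of BMI and CRP. The 2-hour retention figures and the BMI label in Table 7 are minor inconsistencies.

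**What to change.** 1. Check r for each symptom row against the first registry's data, upper abdominal in particular. Then recompute the six rows by ANCOVA. With the printed r (diabetic / Type 2 / post-Nissen / not delayed):
   - GCSI .29 / .47 / .31 / .28
   - Nausea/vomiting .27 / .43 / .29 / .26
   - Fullness .31 / .49 / .33 / .30
   - Bloating .27 / .43 / .29 / .26
   - Upper abdominal .27 / .44 / .30 / .27
   - Hospitalizations .24 / .39 / .26 / .24
2. State in the Table 6 title, footnotes and text that the MDEs are in baseline SD units and assume complete 48-week data in the full subgroups. Bring the footnote's conversion to outcome units into line with that. Restate the summary as a maximum of 0.49 and an average of 0.29.
3. Alternatively, declare the change-score method for the symptom rows and exclude Type 2 versus Type 1 for GCSI and fullness from the sentence. Upper abdominal and hospitalizations would still need recomputing; at its printed r, upper abdominal in that comparison is 0.503, on the boundary.
4. Reconcile the mean, SD and CV for 2-hour retention, including the 0.7 in the text, and make the BMI inequality in Table 7 agree with its label.

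The cost is a correction of table and text, plus a check of r in the existing data. Recruitment, visits and data collection do not change.
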